imbedded in the game ring. Formative work by [name] found that Ring-Fit Adventure™ was the most enjoyable and user-friendly of the 4 evaluated exergames.

C. Rationale

1. The original GameSquad among children and the adapted GameSquad among adolescents with neurodevelopmental and psychiatric diagnoses have both demonstrated strong potential. We now want to further adapt the GameSquad concept for young adults with Down Syndrome.
2. Successful completion of this project represents an initial step in achieving our goal of developing effective interventions to increase MVPA and promote healthy aging in adults with DS.

II. Research Plan and Design

A. Study Objectives: Primary aim: To assess the acceptability, appropriateness, and feasibility of the intervention using quantitative data alongside qualitative data. Specifically, we will assess mins/wk of Ring-Fit Adventure™ played, attendance at virtual health coaching sessions, semi-structured interviews, participant retention, and intervention safety measured as number of adverse events.

B. Secondary aims: To calculate effect sizes for change across 12-wks. in MVPA, physical function, muscular strength, physical activity enjoyment, and self-efficacy.

C. Exploratory aim: To determine energy expenditure of a session of Ring-Fit Adventure™ among adults with DS.

D. Study Type and Design: Single-Group, Pretest-Posttest.

E. Sample size, statistical methods, and power calculation

1. We will calculate point estimates and confidence intervals for all endpoints of interest and will use effect sizes estimated from this data to guide power analyses for future trials. We expect a positive change in MVPA, and in 1 measure of physical function. Continuation to a larger trial will be based on a positive response in at least one of these endpoints.
2. N=20. The sample size was determined from the number of subjects that could feasible be recruited in the 1-year timeline for the grant and within the grant budget.

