F. Subject Criteria (See Vulnerable Populations appendix, if applicable): Primary care physician (PCP) clearance will be required for all participants. A form with PCP clearance will need to be signed before participation will be allowed. Inclusion criteria: 1) Young adults (18-30 yrs.) 2) Diagnosis of DS as determined by a Community Service Provider operating in our recruitment area under the auspices of a Community Developmental Disability Organization (CDDO). 3) Sufficient functional ability to understand directions, communicate preferences, wants, and needs through spoken language. 4) Living at home with a parent/guardian or in a supported living environment with a parent/caregiver who agrees to serve as a study partner. Exclusion criteria: 1) Unable to participate in MVPA. 2) Serious medical risk, e.g., cancer, recent heart attack, stroke, angioplasty as determined by their primary care provider (PCP).

1. Inclusion criteria: 1) Young adults (18-30 yrs.) 2) Diagnosis of DS as determined by a Community Service Provider operating in our recruitment area under the auspices of a

- Community Developmental Disability Organization (CDDO). 3) Sufficient functional ability to understand directions, communicate preferences, wants, and needs through spoken language. 4) Living at home with a parent/guardian or in a supported living environment with a parent/caregiver who agrees to serve as a study partner.
2. Exclusion criteria: 1) Unable to participate in MVPA. 2) Serious medical risk, e.g., cancer, recent heart attack, stroke, angioplasty as determined by their primary care provider (PCP)
 3. Withdrawal/Termination criteria: If at anytime during the intervention, the participant becomes unable to participate in exercise sessions, participation will be terminated by the investigator. If the participant asks to be withdrawn from the study, the participant will be removed.
 4. A study subject can participate in another study while participating in this research study.

E. Specific methods and techniques used throughout the study

1. Laboratory tests: Physical function will be assessed using the 6-minute walk test¹⁶, Timed Up and Go test¹⁷, and the Y-Balance Test¹⁸.
2. Leg strength will be assessed using a standard 5-repetition maximum protocol¹⁹ on a Cybex plate-loaded leg press. Hand grip strength of both the dominant and non-dominant hands will be assessed with a Jamar handgrip dynamometer (JWL Instruments, Chicago, IL)²⁰.

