before each assessment. The device will be programmed utilizing study ID numbers, with no other identifying information. During exercise sessions, participants will breathe into a facemask that directs air into the unit housing the O2 and CO2 analyzers. Data will be retrieved for analysis via a serial port interface and downloaded to a university monitored, HIPPA compliant computer once staff returns to campus. Software provided with the calorimeter will be used to analyze data by aggregating over 20-second epochs for the calculation of 1-min averages. MET levels will be age corrected using the Schofield equation²¹ as recommended by McMurray et al²². Participants will be asked to wear both hip and wrist ActiGraphs during the assessment for comparison of physical activity levels between devices.

4. Timeline:

Timepoint	Action	Duration/Delivery
Week 0	Pre-Testing. 6-minute walk test, Timed Up and Go test, Y-Balance Test. 5-repetition maximum Leg Press, Hand grip strength (both hands). Physical Activity Enjoyment Scale, Self-Efficacy for Activity for Persons with Intellectual Disabilities Scale. RF Set-up Fitbit/iPad Set-Up	120 minutes. Kirmayer Fitness Center
Week 1	Intervention (RF sessions + virtual health coaching session)	90 minutes At home RF sessions, virtual health coaching on zoom.
Week 2	Intervention (RF sessions + virtual health coaching session)	120 minutes At home RF sessions, virtual health coaching on zoom.
Week 3	Intervention (RF sessions + virtual health coaching session)	150 minutes At home RF sessions, virtual health coaching on zoom.
Weeks 4-12	Intervention (RF sessions + virtual health coaching session)	180 minutes At home RF sessions, virtual health coaching on zoom.
Week 13	Post-Testing 6-minute walk test, Timed Up and Go test, Y-Balance Test. 5-repetition maximum Leg Press, Hand grip strength (both hands). Physical Activity Enjoyment Scale, Self-Efficacy for Activity for Persons with Intellectual Disabilities Scale.	120 minutes. Kirmayer Fitness Center

	Qualitative Interview	
	Energy Expenditure Test (Cosmed)	

Time frame for completion: Months 1-5: Recruit participants, complete the 12-week pilot trial of GameSquadDS, and conduct post intervention semi-structured interviews. Month 6: Complete data analysis for all process and physical outcomes.

F. Risk/benefit assessment:

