 - e. Safety-related triggers that would cause the PI to stop or alter the study: The most likely scenario indicating the need to stop the investigation would be a failure to recruit or deliver the intervention as planned. Another issue relating to stopping rules for this trial would be new information. It is unlikely that any new information will become available during this trial that would necessitate stopping the trial
2. Data on adverse events will be reported monthly to the PI throughout this trial. We anticipate that most adverse events will be mild in nature and will allow a complete return to the same activities after a short period of time; that is, later that day or a day or two later.
3. We anticipate most adverse events (if not all) will allow a complete return to the same activities after a short period of time; that is, later that day or a day or two later. However, if a serious adverse event that prohibits participation moving forward, the participant will be terminated from the intervention.

III. Subject Participation

A. Recruitment:

1. The recruitment plan was informed by our experience with completed projects where we successfully recruited adults with DS (DK083539, HD094704, AG036909). As in our previous trials, project staff will contact local community agencies serving adults with DS, case managers, and CDDOs by mail or email, provide presentations at CDDO meetings, and text for CDDO newsletters describing the project. Interested adults with DS or their parent/caregiver will be asked to contact the study coordinator via email, our website, or a dedicated toll-free study phone number that will be included in all recruitment materials. The study coordinator will contact interested individuals by phone to answer questions and conduct an initial eligibility screen. Zoom® meetings will be scheduled with those remaining interested and potentially eligible to complete eligibility screening and to obtain informed consent or parent/guardian consent and participant assent in cases where the participant has a surrogate decision maker. We will attempt to recruit ~50% female and ≥ 30% minorities. Study staff will forward a form to the PCP requesting permission to participate.

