coordinator. Data will be linked by participant ID. Identifiable information and outcome data will be stored separately. Only de-identified data will be available to study personnel.

C. Quality Assurance / Monitoring

1. Research personnel will be observed by co-investigators for their first three sessions. Feedback will be given to ensure future sessions go as planned.
2. There are no plans to have third-party monitoring.

V. Data Analysis and Reporting

A. Statistical and Data Analysis: We will calculate point estimates and confidence intervals for all endpoints of interest and will use effect sizes estimated from this data to guide power analyses for future trials. We expect a positive change in MVPA, and in 1 of the measures of physical function. Continuation to a larger trial will be based on a positive response in at least one of these endpoints.

Thematic analysis will be used to analyze qualitative data completed by research personnel²³.

B. Outcome: We expect a positive change in MVPA, and in 1 of the measures of physical function. Continuation to a larger trial will be based on a positive response in at least one of these endpoints.

C. Study results to participants: All results will be given to the subjects after completion of the post-testing appointment. An interview will be given going over the results and giving the participants a hand-out of all outcomes. This is due to the potential of positive results after being physically active, and could have ramifications on future behavior.

D. Publication Plan: Publication will be sought as a pilot, feasibility study based on quantitative and qualitative results from all outcomes.

Bibliography / References / Literature Cited

2. Changes in cognitive function after a 12-week exercise intervention in adults with Down syndrome.

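### The stopping rule in Subject Criteria (II.F.3) does not say whether people who become unable to exercise stay in the study for the Week 13 interview and questionnaires, and it must be reconciled with II.I.3

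*Combined protocol and SAP*

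**What the plan says.** Section II uses the letters E and F twice. II.F.3 here means item 3 of Subject Criteria, and the timeline is item 4 of the specific methods section that follows it.

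- **II.F.3, withdrawal and termination:** "If at anytime during the intervention, the participant becomes unable to participate in exercise sessions, participation will be terminated by the investigator". The next sentence reads: "If the participant asks to be withdrawn from the study, the participant will be removed".
- **II.I.3, adverse events:** "if a serious adverse event that prohibits participation moving forward, the participant will be terminated from the intervention". The same item expects such cases to be uncommon: "We anticipate most adverse events (if not all) will allow a complete return to the same activities after a short period of time".
- **II.A, primary aim:** besides minutes of play, the measures are "attendance at virtual health coaching sessions, semi-structured interviews, participant retention, and intervention safety measured as number of adverse events". That makes five measures, of which the interviews are one.
- **Timeline:** the qualitative interview appears only in the Week 13 row. The enjoyment and self-efficacy questionnaires and the function and strength tests appear only at Weeks 0 and 13. The text under the table says the team will "conduct post intervention semi-structured interviews".
- **V.A, analysis:** the team "will use effect sizes estimated from this data to guide power analyses for future trials". No analysis set or missing-data rule is given.

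**The concern.** A participant who has a serious adverse event and can no longer do the sessions meets both rules. One rule ends *participation*, with no object stated; the other ends the *intervention*. A coordinator with only these two sections cannot tell whether to contact that person at Week 13.

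The pilot's primary aim is acceptability, appropriateness and feasibility. Someone who became unable to do the sessions knows something about feasibility that completers cannot report, and with 20 participants in a single arm there is no other source for it. If that person is not interviewed, the account is lost for good. The enjoyment and self-efficacy effect sizes would also rest on those who could continue.

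**Working it through.** **Step 1. Compare the two rules.**

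| | II.F.3 | II.I.3 |
|---|---|---|
| Trigger | Any inability to do exercise sessions during the intervention | A serious adverse event that prevents taking part |
| What ends | Participation, object unstated | The intervention |
| Stays for Week 13? | Not stated | Not stated |

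The triggers are not identical, but a serious adverse event that prevents exercise meets both.

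**Step 2. What is lost if II.F.3 ends study participation.** Lost: the qualitative interview, and the Week 13 questionnaires and tests. Not lost: Fitbit data, play minutes, coaching attendance and adverse events up to stopping. Retention can still be counted. The eligibility screening interview and the meeting to feed back results serve other purposes and do not replace the qualitative interview.

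**Step 3. How many people.** The documents give N = 20 and no stopping rate, so the per-person risk p is assumed. The chance that at least one of 20 is affected is 1 − (1 − p)^20:

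- p = 1%: 18%
- p = 2%: 33%
- p = 5%: 64%
- p = 10%: 88%

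The expected number is 20p: 0.2, 0.4, 1 and 2. Physician clearance, the exclusion criteria and the expectation in II.I.3 point to the low end, so 0 or 1 is plausible.

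**Step 4. Size of the numerical bias.** The plan states no figure to reproduce. Let completers gain g and let the k people who stop decline by d, both in SD of change. The all-enrolled mean is [g(20 − k) − dk]/20, so the completers' mean exceeds it by k(g + d)/20. The 95% CI half-width is t(0.975, n − 1)/√n with n = 20 − k: 2.101/√19 = 0.482 for k = 1, and 2.110/√18 = 0.497 for k = 2. All values of g, d and k are assumptions.

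| k | g | d | Bias (SD) | Bias / half-width |
|---|---|---|---|---|
| 1 | 0.5 | 0 | 1 × 0.5/20 = 0.025 | 5% |
| 1 | 0.5 | 0.5 | 1 × 1.0/20 = 0.050 | 10% |
| 1 | 0.2 | 0 | 1 × 0.2/20 = 0.010 | 2% |
| 2 | 0.5 | 0 | 2 × 0.5/20 = 0.050 | 10% |
| 2 | 0.5 | 0.5 | 2 × 1.0/20 = 0.100 | 20% |

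The bias is zero if those who stop change as completers do. It has no fixed upper limit, because it grows with k and with any worsening.

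**Step 5. Could the sign of a mean change reverse?** That needs d > g(20 − k)/k. For k = 1 this is 0.5 × 19 = 9.5 SD, or 0.2 × 19 = 3.8 SD at the smaller gain. Neither is realistic for one person.

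**The case against.** The best defence is that the two sections say the same thing. II.I.3 speaks of an event that prevents participation and then ends only the intervention, so there the word means taking part in the sessions. II.F.3 itself uses a different expression, withdrawal from the study, when a participant asks to leave. An interview described as taking place after the intervention can also include someone whose intervention ended early. This stands, and it is why the wording is ambiguous and not a flat contradiction. It does not close the gap: even on this reading, no available text says that people who stop are still interviewed or re-assessed.

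A reader might go further and infer that the plan has decided against any exit assessment. The documents do not support that. It would be an inference from silence, and the consent pages, which might address contact after stopping, are not in the available text.

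It is also fair to object that adverse events are reported monthly, so some information on these stops is captured anyway. That is true of the event itself, but not of the participant's view of acceptability and feasibility.

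**Conclusion.** The point holds as a cheap improvement of minor severity. Two rules with overlapping triggers end different things, and the literal reading of II.F.3 loses primary-aim interview data from the people best placed to say why the programme could not be continued. Probably 0 or 1 of 20 would be affected, which is a judgement from the eligibility rules and II.I.3 and not a documented rate. The bias of 0.025 SD at 1 of 20 rests on an assumed completer gain of 0.5 SD and no change in the person who stops; it is larger if that person worsens.

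Two stronger conclusions are tempting. The first is that the effect sizes, or the rule that "Continuation to a larger trial will be based on a positive response in at least one of these endpoints", are in jeopardy. With one person stopping, the bias is a small fraction of the sampling error at this sample size. MVPA, one of the continuation endpoints, is recorded by Fitbit throughout the intervention. The second is that everyone who disengages is removed. The rule covers inability to exercise, not people who dislike the game or play little.

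**What to change.** 1. In II.F.3, define separately stopping the intervention and leaving the study, and use the same terms in II.I.3. Leave unchanged when exercise must stop.
2. State that, unless consent is withdrawn, people who stop the intervention are offered the existing semi-structured interview and the enjoyment and self-efficacy questionnaires, by Zoom if needed. The study already uses Zoom for consent and coaching.
3. In V.A, state that their data enter the thematic analysis and the enjoyment and self-efficacy estimates, and that the number without Week 13 data is reported with reasons.

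No proposal is made on physical testing after stopping. The only clearance described is the physician's, before enrolment, so the documents give no basis for one. Any bias in function and strength would therefore remain.

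The cost is protocol and consent wording, a few short interviews by existing staff (none if nobody stops), and possibly slightly less favourable estimates.

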2. Primary aim: To assess the acceptability, appropriateness, and feasibility of the intervention using various quantitative alongside qualitative data. Specifically, we will assess mins/wk of Ring-Fit Adventure™ played, attendance at virtual health coaching sessions, semi-structured interviews, participant retention, and intervention safety measured as number of adverse events.

Secondary aim: To calculate effect sizes for change across 12-wks. in MVPA, physical function, muscular strength, physical activity enjoyment, and self-efficacy. We hypothesize increases in MVPA, physical function, muscular strength, physical activity enjoyment, and self-efficacy.

Secondary aim: To determine energy expenditure of a session of Ring-Fit Adventure™ among adults with DS. We hypothesize energy expenditure akin to moderate physical activities.

B. Background and Significance

1. Study Significance: Down syndrome (DS) or trisomy 21 is the most common chromosomal abnormality associated with an intellectual disability (ID). The current incidence of DS is 1 in every 650 live births which is ~30% higher than in 1979, largely due to women conceiving after age 35. Additionally, life expectancy for people with DS has increased dramatically over the past 60 years due to advancements in disease knowledge, medical care, and caregiving services⁹. With this increase in DS prevalence through improved life expectancy, it is critical to address ways to support healthy living throughout their lifespan. Adults with DS have a higher prevalence of obesity¹⁰ and obesity associated health conditions including sleep apnea and type 2 diabetes¹¹ compared to adults without DS. Additionally, adults with DS face premature aging¹², higher rates and earlier onset of Alzheimer's disease (AD)¹³, functional decline, mobility restrictions, frailty, musculoskeletal problems, osteoporosis, and sleep problems when compared with typically developed adults¹⁴. These increased rates of chronic disease and functional decline are associated with reduced quality of life, and increased burden on families, care providers, and disability services. Chronic disease also contributes to absenteeism from disability employment, premature withdrawal from the workforce, and increased health care utilization¹⁵.

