2. We recently asked 10 adults with DS who visited our lab to complete assessments for an on-going trial (TL1TR002368) to play the introductory game on Ring-Fit Adventure™ for ~15 minutes while wearing a portable accelerometer on a belt at waist. Approximately 7 minutes provided instructions on how to use the game and ~8 minutes predominately light physical activity active play. Participants enjoyed playing the game and felt the game would be feasible and safe for home use. The accelerometer data indicated ~5 minutes of light and ~3 minutes of MVPA, which appeared reasonable based on the types of activities included in the game. Thus, based on these preliminary results we propose to adapt the GameSquad intervention using the Ring-Fit Adventure™ as our exergaming platform for use in transition age young adults with DS (18-25 yrs.)
3. Literature Review: A 24-wk. randomized trial in 46 children with overweight/obesity using a home-based intervention which incorporates exergaming (Xbox Kinect) with individual health coaching called GameSquad demonstrated reduced BMI-z score ($p=0.016$) and improved systolic and diastolic blood pressure, total and low-density lipoprotein cholesterol, and MVPA relative to wait-list control (all $p < 0.05$)⁷. Members of our study team recently conduct a 10-wk pilot trial of the game GameSquad intervention (3 exergaming sessions/wk., plus 6 health coaching sessions) adapted for use with adolescents with neurodevelopmental and psychiatric diagnoses ($n=23$, age ~ 15 yrs.)⁸. Participants reported an average of ~82 min/wk. of exergaming and completed 83% of the scheduled health coaching sessions. Unfortunately, both the original and Adaptive GameSquad interventions used the Xbox Kinect gaming system which was discontinued in 2017. Nintendo Ring-Fit Adventure™ is a novel, and currently popular exergame that uses both a resistance ring and body weight to perform numerous upper and lower body cardiovascular and resistance exercises. In contrast to other exergames, participants incorporate exercise to complete an adventure narrative guided by Ring-Fit Adventure™ characters. The narratives provide ~60 hours of unique activity which increases in both intensity and difficulty as participants progress through the game. Participant exercise is guided by both written instructions and visual demonstrations via an in-game avatar. Feedback regarding proper exercise form is provided by controllers/ accelerometers

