3. **Daily physical activity, specifically MVPA, will be assessed using a Fitbit that will be synced to a tablet computer (iPad). Daily physical activity across the 12-week study activity will be assessed using a Fitbit Versa 3 monitor worn on the non-dominant wrist during each day of the intervention. Real-time data from the Fitbit will be transferred via Fitbit's Open API using R, thus participant burden is minimal. Immediate participant feedback via a graphic display of daily steps, minutes of sedentary time, time spent in light, moderate and vigorous PA will be available on the iPad. This data, accessible to health educators, will be used to provide motivation and feedback during the virtual coaching sessions. Participants will be reminded to wear and charge the Fitbit during the individual support/education sessions and will receive automatic reminder messages via the iPad.**

Study Procedures: 6-minute walk test (6-minutes), Timed Up and Go test (5-minutes), and the Y-Balance Test (5-minutes). Leg strength will be assessed using a standard 5-repetition maximum protocol (5-minutes) on a Cybex plate-loaded leg press. Hand grip strength of both the dominant and non-dominant hands will be assessed with a Jamar handgrip dynamometer (JWL Instruments, Chicago, IL), (5-minutes). Physical activity enjoyment will be assessed using the Physical Activity Enjoyment Scale (10-minutes). Self-efficacy will be assessed using the Self-Efficacy for Activity for Persons with Intellectual Disabilities Scale (10-minutes). Energy expenditure of a ring-fit session will be assessed in a volunteer sample of both patient and caregiver using a previously validated portable, open-circuit indirect calorimeter (Cosmed, Italy) which measures breath-by-breath ventilation, expired oxygen, and carbon dioxide. Study staff will schedule the assessment with participants which will involve a visit to the lab. The flow turbine will be calibrated using a 3.0-L syringe. The lightweight (~1.5 kg) portable system will be attached by a harness around the waist and shoulders of the participant

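### No MVPA wear is planned before the intervention and no pre or post MVPA window is defined, so the planned data support only a within-intervention trend

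*Combined protocol and SAP*

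**What the plan says.** - **Design and aim.** Section II.D describes the study as "Single-Group, Pretest-Posttest". The secondary aim (I.A.2, repeated in II.B) is "To calculate effect sizes for change across 12-wks. in MVPA" and in function, strength, enjoyment and self-efficacy. I.A.2 hypothesizes an increase in each.
- **Use of the result.** Sections II.E (sample size) and V.A say that the estimated effect sizes will guide power analyses for future trials. They make continuation depend on a positive response in MVPA or in one physical function measure.
- **MVPA instrument.** The section on specific methods, item 3, assigns daily MVPA to a "Fitbit Versa 3 monitor worn on the non-dominant wrist during each day of the intervention". The iPad shows participants their activity. Of the same data the protocol says: "This data, accessible to health educators, will be used to provide motivation and feedback during the virtual coaching sessions".
- **Timeline.** Week 0 lists the function, strength and questionnaire tests and then "RF Set-up Fitbit/iPad Set-Up". Week 13 repeats those tests and adds the interview and the energy-expenditure test. MVPA is in neither list. Scheduled time is 90, 120 and 150 minutes in Weeks 1 to 3 and 180 minutes in each of Weeks 4 to 12.
- **Other activity monitors.** In the energy-expenditure test only: "Participants will be asked to wear both hip and wrist ActiGraphs during the assessment for comparison of physical activity levels between devices".
- **Hand-over.** Section III.F provides the Fitbit, game and console together, after the pre-testing appointment.
- **Analysis.** Section V.A promises point estimates and confidence intervals. It gives no MVPA baseline window, end window or valid-wear rule.

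**The concern.** A pretest-posttest effect size needs a level measured before exposure. For MVPA none is planned. The first planned Fitbit day is an intervention day, when participants may already be playing, being coached and seeing their own activity on the iPad. There is no control group from which the untreated level could be inferred.

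The analyst would have to choose a reference period after the data are in, and the earliest intervention days are the obvious choice. Game MVPA already present in those days is then subtracted from the effect. At stake are the MVPA effect size that is meant to size the next trial and the MVPA half of the continuation rule. No later analysis can recover a level that was not recorded.

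**Working it through.** **1. Where each change outcome is measured** (timeline and specific methods)

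| Outcome | Week 0 | Weeks 1-12 | Week 13 |
|---|---|---|---|
| Physical function | yes | no | yes |
| Strength | yes | no | yes |
| Enjoyment, self-efficacy | yes | no | yes |
| MVPA (Fitbit) | set-up only | daily | not listed |

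MVPA is the only change outcome without a planned measurement on both sides of the intervention. There are 0 planned wear days before it and 0 after it.

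**2. What a Week 1 reference would recover (illustration)**

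The plan names no contrast, so this takes Week 1 against Week 12, full adherence to scheduled minutes and other activity unchanged.

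Inputs:
- Scheduled minutes: 90 in Week 1 and 180 in Week 12 (timeline). The entries cover play and coaching.
- c = coaching minutes per week inside that time. The length of a coaching session is not given, so c is assumed to be 0, 15 or 60.
- y = MVPA minutes per minute of play. Section I.B.2 reports a session of about 15 minutes, of which about 8 were active play: "The accelerometer data indicated ~5 minutes of light and ~3 minutes of MVPA". This gives 3/15 = 0.20 over the whole session and 3/8 = 0.375 over active play. A rising yield is considered because section I.B.3 describes "unique activity which increases in both intensity and difficulty as participants progress through the game".

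Share of the true gain recovered = 1 − [(90 − c) × y₁] / [(180 − c) × y₂]

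| Yield | c | Calculation | Share |
|---|---|---|---|
| constant | 0 | 1 − 90/180 | 50% |
| constant | 15 | 1 − 75/165 | 55% |
| constant | 60 | 1 − 30/120 | 75% |
| 0.20 rising to 0.375 | 0 | (67.5 − 18)/67.5 | 73% |
| 0.20 rising to 0.375 | 60 | (45 − 6)/45 | 87% |

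With Week 4 as the reference and constant yield, scheduled time is 180 minutes at both ends and the share is 0.

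**3. If play does not follow the ramp**

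Section I.B.3 reports about 82 min/wk of exergaming in the earlier adolescent pilot. If play were level at 82 min/wk with constant yield, the Week 1 to Week 12 change would be 0. The true gain would be 82 × 0.20 = 16.4 to 82 × 0.375 = 30.75 min/wk. If play fell after Week 1, the apparent change would be negative although the gain over a true baseline is positive.

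**4. Effect on the next trial's sample size**

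If the SD of change is the same under both references, required n scales as 1/share²: 1/0.50² = 4.0, 1/0.733² = 1.86 and 1/0.867² = 1.33. As an example, assume a true paired effect of 0.5 with 80% power and two-sided 5%. The paired t-test then needs 34 participants. At the attenuated effects:
- 0.5 × 0.50 = 0.25: n = 128
- 0.5 × 0.733 = 0.367: n = 61
- 0.5 × 0.867 = 0.434 (rounded up): n = 44

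**The case against.** **The aim may mean a trend.** Change across 12 weeks could be read as a trend within the intervention, and the pretest-posttest label is met by the Week 0 and Week 13 tests. The wording does allow this. But the same sentence covers outcomes that are measured before and after, and under either reading the MVPA contrast is undefined. If a trend is intended, the plan should say so.

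**Set-up at Week 0 may yield some days before Week 1.** That is possible, and the interval between the two is not stated. Such days are not required, not defined as baseline and not play-free by design, since game and console are handed over at the same time.

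**The magnitudes are soft.** This stands. The yields come from one introductory session in 10 adults wearing a waist accelerometer, whereas the endpoint uses a wrist Fitbit. About 7 of the 15 minutes were instructions, which need not persist through Week 1. The 82 min/wk comes from a different population and gaming system. The SD of change may differ between reference periods. The well-grounded figure is that Week 1 already holds 90 of the 180 minutes scheduled for Week 12.

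**The ramp could produce a positive response.** Also true: a rise from Week 1 is partly written into the schedule and could satisfy the continuation rule. With other activity unchanged and some MVPA from play in Week 1, that rise still understates the gain over a true baseline. It is thus a poor guide both to continuation and to effect size.

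**This is a 20-person feasibility pilot.** The primary aim is untouched, and function tests alone can satisfy continuation. That limits the severity but does not remove the gap.

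**Conclusion.** The concern holds. The plan collects no pre-intervention MVPA and defines no MVPA contrast, so change from a pre-intervention level cannot be estimated from the planned data. This follows from the measurement schedule and depends on none of the illustrative figures.

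The size depends on a contrast that the plan does not name. With Week 1 as the reference, full adherence and unchanged other activity, 50% of the gain is recovered on scheduled minutes alone and 55% to 87% under the other assumptions about coaching time and yield. Level play with constant yield recovers none. A next trial sized on shares of 50%, 73% or 87% would need about 4.0, 1.9 or 1.3 times the participants, if the SD of change is unchanged.

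The damage is confined to the MVPA effect size and the MVPA part of the continuation rule. It should be fixed before enrolment.

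**What to change.** 1. Start Fitbit wear at the Week 0 visit and collect about 7 days before the first Ring-Fit session and the first coaching call, with the iPad activity display off. Seven days is a convention that covers each day of the week; it is not derived from the protocol.
2. Game set-up can stay at Week 0 if participants are told that play starts after the baseline week. Minutes played are already a primary-aim measure, but the protocol does not say how or from when they are recorded. Recording should run from set-up so that early play can be detected.
3. Define baseline MVPA as mean min/day over valid days in that week, with a stated minimum wear time per day and minimum number of valid days. Define follow-up MVPA by the same rule over the last 7 days of Week 12.
4. Name this contrast in section V.A and add both windows to the timeline.
5. If a baseline week is not possible, describe MVPA as a within-intervention trend and remove it from the continuation rule. This needs only a change of text.

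**Cost.** Zero to one extra week per participant, depending on how long before Week 1 the Week 0 visit falls. Months 1-5 in the timeline are 5 × 365.25/12/7 = 21.7 weeks. Weeks 0 to 13 use 14, leaving 7.7 for staggered recruitment, or 6.7 with one added week. The sample-size section refers to a 1-year grant timeline, which would leave more room. No new device is needed, and no extra visit if set-up stays at Week 0. Some reactivity to wearing the device will remain in the baseline week, and the no-play instruction relies on adherence.
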